15.2. SECONDARY EFFICACY

The secondary efficacy analyses will be performed for the FAS. Patients withdrawn after only one treatment period will not be included in the analyses of any of the secondary efficacy variables.

15.2.1. SECONDARY EFFICACY VARIABLES & DERIVATIONS

15.2.1.1. Change in baseline in average FEV_1 of AUC_{0-4h} (Average FEV_1 over 4 hours), average FEV_1 of AUC_{0-12h} (Average FEV_1 over 12 hours) and (morning) trough FEV_1 on Day 7 (Secondary variables 1, 2 and 3)

Average FEV_1 is defined as the AUC_{0-4h} FEV_1 collected, divided by the length of the time (in hours). AUC_{0-4h} FEV_1 is derived using the following formula:

$$AUC = \frac{1}{2}(t_1 - t_0)(y_1 + y_0) + \frac{1}{2}(t_2 - t_1)(y_2 + y_1) + \dots + \frac{1}{2}(t_i - t_{i-1})(y_i + y_{i+1})$$

where i are the number of intervals, t_i are the time values or time intervals (in actual hours) between assessments and y_i the FEV_1 values (highest of the three acceptable readings) at t_i . The AUC result will then be divided by the actual time (the time elapsed since dosing, until the time of assessment) at 4-hour assessment (as this can occur ± 10 minutes) to obtain the average FEV_1 . If the assessment at 4-hour is missing, the AUC result will be divided by the actual time of the last collected assessment. For analysis purposes, it will be assumed that the pre-dose value (immediately pre-dose) occurred at time 0 when computing PD parameters. If a patient misses hour 2 and 4 then the AUC_{0-4} is set to missing.

Descriptive statistics (see [Appendix 1](#) [Programming conventions for outputs]) for AUC_{0-4} will be presented for all patients assigned to FAS, at each assessment and change from baseline at each assessment as relevant. All summaries will be presented for each treatment group.

Change from baseline FEV_1 to FEV_1 AUC_{0-4} will be derived to test the hypothesis described in [Section 15.2.3](#) with

Document: Z:\RPL554\AZA40375\Biostatistics\Documentation\SAP\Verona RPL554-DP-201 SAP v2.0 – Part B

Author: [name] / [name]

Version Number: 2.0

Version Date: [08JUL2019]

Template No.: CS_TP_BS016 Revision 5

Reference: CS_WI_BS005

Effective Date: 01Apr2018

Copyright © 2009, 2010, 2012, 2016, 2018 IQVIA. All rights reserved. The contents of this document are confidential and proprietary to IQVIA Holdings Inc. and its subsidiaries. Unauthorized use, disclosure or reproduction is strictly prohibited.

baseline defined as the average of the FEV₁ pre-dose assessments (-60 minutes and -5 minutes) collected.

AUC_{0-12h} FEV₁ is defined and derived similarly to AUC_{0-4h} above, but over 12-hours post-dose. If patient misses hours 11 and 12 then the AUC_{0-12h} is set to missing.

Morning trough FEV₁ is the average of the FEV₁ pre-dose assessments (-60 minutes and -5 minutes) on Day 7 and the change from baseline will be analyzed similarly to AUC_{0-4h} and AUC_{0-12h}.

15.2.1.2. Change in baseline in peak FEV₁ measured after first dose, average FEV₁ of AUC_{0-4h} on Day 1 and average FEV₁ of AUC_{0-12h} FEV₁ on Day 1 (Secondary variables 4, 5 and 6)

Peak FEV₁ measured after first dose is defined as the peak FEV₁ (after 4 hours of dosing) on Day 1. It is defined as the change from baseline to peak FEV₁ and derived similarly to primary analysis (see [section 15.1.1](#)), but instead at Day 1.

AUC_{0-4h} FEV₁ and AUC_{0-12h} FEV₁ on Day 1 are defined and derived similarly to secondary endpoint above (see [section 15.2.1.1](#)), but at Day 1. Parameters will be calculated over 4 and 12 hours, respectively (on Day 1 of each treatment period). If patient misses hours 2 and 4 then the AUC_{0-4h} is set to missing. Similarly, if patient misses hours 11 and 12 then the AUC_{0-12h} is set to missing. If the assessment at 12-hours is missing, the AUC result will be divided by the actual time of the last collected assessment.

15.2.1.3. Determination of onset of action (>10% increase in FEV₁, from pre-first dose, censored at 120 minutes) on Day 1 (Secondary variable 7)

Onset of action is defined as a >10% increase in FEV₁ from pre-dose on Day 1 over the next 120 minutes (2 hours) after morning dosing on Day 1 (5, 15 and 30 minutes and 1, 1.5, 2 hours). Time to onset will be derived as the time to onset of action is achieved. For analysis purposes, it will be assumed that the pre-dose value occurred at time 0. Patients not experiencing an onset of action will be censored at 120 minutes (2 hours) or at time of premature discontinuation (if withdrawn before 120 minutes). If the number of patient censored regarding onset of action is deemed to be too high (number of patients with onset of action censored >50%), the Kaplan-Meier estimates and

Document: Z:\RPL554\AZA40375\Biostatistics\Documentation\SAP\Verona RPL554-DP-201 SAP v2.0 – Part B

Author: [name] / [name]

Version Number: 2.0

Version Date: [08JUL2019]

Template No.: CS_TP_BS016 Revision 5

Reference: CS_WI_BS005

Effective Date: 01Apr2018

Copyright © 2009, 2010, 2012, 2016, 2018 IQVIA. All rights reserved. The contents of this document are confidential and proprietary to IQVIA Holdings Inc. and its subsidiaries. Unauthorized use, disclosure or reproduction is strictly prohibited.

accompanying figure will not be presented. Patients receiving placebo will not be summarized in either tables or figure.

15.2.1.4. RPL554 steady state pharmacokinetics (AUC_{0-12h}, Cmax, time to maximum concentration [tmax]) (Secondary variable 8)

Concentration of RPL554 and computed PK parameters (AUC_{0-12h}, C_{max} [maximum concentration], t_{max} [time to maximum concentration]) on Day 7 of each treatment period (pre-dose, 30 minutes and 1, 1.5, 2, 4, 8 and 12-hours post dose).

15.2.1.5. Change from baseline in rescue medication use during treatment periods (Secondary variable 9)

The average use, in terms of weight (mcg) of rescue medication during the treatment periods will be collected from the Rescue Medication Canister Dispensed and Rescue Medication Canister Weight eCRF pages and will be summarized by treatment group. Rescue medication used will be calculated from the difference in weight at time of dispensing and weight at time of collection. So, change from baseline is the difference in rescue medication from baseline (at pre-dose on Day 1) and the collection visit (12hr post-dose on Day 7).

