9.4.5 Efficacy/Pharmacodynamics

FEV₁ and FVC will be summarized as actual value and change from baseline using descriptive statistics over time for all treatments and both study parts.

The peak effect on FEV₁ during these time intervals will be computed as the maximum value in the 4 hours after dosing. The average effect (average FEV₁ AUC_{0-t}) will be calculated as the AUC divided by the length of the time interval of interest. For analysis of the peak, average and trough FEV₁, the change from baseline will be expressed as the parameter divided by the pre-dose Day 1 baseline value.

In Part A, computed pharmacodynamic parameters for FEV₁ will be compared between the treatments using analysis of covariance models with fixed factor treatment, and using the pre-dose baseline value as a covariate. In Part B, computed pharmacodynamic parameters (peak, AUC₀₋₄, AUC₀₋₁₂ and trough) for FEV₁ will be compared between the treatments using analysis of covariance models adjusting for treatment period and patient, and using the pre-dose Day 1 baseline value as a covariate. FEV₁ will be analyzed using multiplicative models, which means that data (dependent and baseline) are logged prior to analysis and the result then transformed back to the linear scale giving treatment differences as ratios of geometric means.

Primarily, active treatments will be compared to placebo. For RPL554 DPI, the high dose will first be compared to placebo, and if found statistically significant then the next lower dose will be compared to placebo, and if found statistically significant then the subsequent lower dose will be compared to placebo, and this procedure repeated for all doses. Secondarily, the different doses of RPL554 DPI will be compared. Results of the comparisons will be expressed as the mean geometric ratio with 95% confidence intervals and associated, 2-sided, p-value.

Onset of action will be calculated and summarized by treatment. In Part B, a Kaplan-Meier plot illustrating time to onset will be constructed and from the survival curves the median time to onset will be estimated. Placebo will not be included in summaries of onset of action.

In Part B, the average use of rescue medication during the treatment periods will be summarized by treatment group. In addition, all rescue medication used during the treatment visits (Day 1 in Part A and Days 1 and 7 in Part B) will be listed to assess the accuracy of the FEV₁ recordings.

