2.2. SECONDARY OBJECTIVES

The secondary objectives of this part are as follows:

- To investigate the safety and tolerability of repeat doses of RPL554 administered by DPI.
- To investigate the bronchodilator effect of RPL554 administered by DPI, in terms of average FEV₁ area under the curve (AUC)_{0-4h}, average FEV₁ AUC_{0-12h} and trough FEV₁.
- To determine the onset of action of RPL554 administered by DPI.
- To evaluate the PK profile of RPL554 administered by DPI.
- To evaluate the amount of rescue medication use during treatment periods.

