Summary statistics for each parameter will be presented for baseline, at point of interest (if applicable) and change from baseline by treatment group on patients with both assessments, on the original scale.

Document: Z:\RPL554\AZA40375\Biostatistics\Documentation\SAP\Verona RPL554-DP-201 SAP v2.0 – Part B

Author: [name] / [name]

Version Number: 2.0

Version Date: [08JUL2019]

Template No.: CS_TP_BS016 Revision 5

Reference: CS_WI_BS005

Effective Date: 01Apr2018

Copyright © 2009, 2010, 2012, 2016, 2018 IQVIA. All rights reserved. The contents of this document are confidential and proprietary to IQVIA Holdings Inc. and its subsidiaries. Unauthorized use, disclosure or reproduction is strictly prohibited.

15.2.3.2. Analysis of Secondary Variable 7

Onset of action will be summarized by treatment and a Kaplan-Meier plot illustrating time to onset constructed. The SAS® procedure LIFETEST, will be used as follows to calculate the median, 25th and 75th percentile:

```
PROC LIFETEST DATA=... OUTSURV =... CONFTYPE = LINEAR METHOD =  
KM ALPHA = 0.05 ALPHAQT = 0.05 PLOTS = (SURVIVAL (FAILURE NOCENSOR));  
    TIME ONSET*STATUS (1);  
    STRATA TREATMENT;  
RUN;
```

where ONSET = time to onset of action

TREATMENT = treatment group (Respective dose of RPL554, 150 μ g, 500 μ g, 1500 μ g and 3000 μ g)

STATUS (1) = indicates an event of onset of action

To calculate the mean difference to RPL554 3000 μ g, the SAS procedure LIFETEST will be carried for each treatment comparison pair individually.

If a patient does not have onset of action from pre-dose on Day 1 over the next 120 minutes (2 hours) the data will be censored at 120 minutes or if a patient prematurely discontinued before 120 minutes, the last available assessment time post-dose (1 indicates censored variables). Median differences to the highest dose (RPL554 3000 μ g) will be estimated and the p-value based on the PROC LIFETEST above (Wilcoxon signed rank sum test) between each treatment groups and the highest dose will also be presented.

15.2.3.3. Analysis of Secondary Variable 8

As described in [section 4.3](#), this SAP will not summarise the analyses related to the PK concentrations and parameters and this will be handled by a third-party vendor.

15.2.3.4. Analysis of Secondary Variable 9

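### SAP Part B drops the Kaplan-Meier onset results when more than half of patients are censored, so their display depends on the onset result itself

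*SAP*

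**What the plan says.** SAP Part B 2.2 lists as a secondary objective "To determine the onset of action of RPL554 administered by DPI". Section 15.2.1.3 defines onset as a >10% rise in FEV1 from pre-dose, assessed "after morning dosing on Day 1 (5, 15 and 30 minutes and 1, 1.5, 2 hours"). It then sets the censoring rule: "Patients not experiencing an onset of action will be censored at 120 minutes (2 hours"), or at the time of discontinuation if that comes earlier.

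The same section adds the display rule. If censoring is judged too high, specified as the "number of patients with onset of action censored >50%), the Kaplan-Meier estimates and" "accompanying figure will not be presented".

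Two other places promise the same output with no condition:

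- Protocol 9.4.5: "a Kaplan-Meier plot illustrating time to onset will be constructed and from the survival curves the median time to onset will be estimated".
- SAP Part B 15.2.3.2: "Onset of action will be summarized by treatment and a Kaplan-Meier plot illustrating time to onset constructed". PROC LIFETEST is specified there to "calculate the median, 25th and 75th percentile".

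SAP Part B 3.3, which should list changes from the protocol analysis, says there are none.

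**The concern.** The rule ties the display of a planned result to the value of that result. The first dose of each period is given in clinic and the window is two hours, so almost the only way to be censored is not to respond. A dose on which most patients fail to reach the threshold loses its curve and quartiles; a dose on which most reach it keeps them. A reader of the report would then see Kaplan-Meier results drawn preferentially from the better-responding doses, or none at all, across a 20-fold dose range (150 to 3000 µg).

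Two ambiguities add to this. The SAP does not say whether the 50% is counted within a dose or over all doses. It also describes the censored number as something to be judged too high, which leaves room for discretion beside the numeric cut.

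**Working it through.** **Passages side by side.** Protocol 9.4.5: plot and median, no condition. SAP 15.2.3.2: plot and quartiles, no condition. SAP 15.2.1.3: estimates and figure only if at most 50% are censored. SAP 3.3: no changes. The SAP departs from the protocol, disagrees with itself, and does not declare the departure.

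**Inputs.** The number per dose is 30, the completion target in protocol 4.3.4 and 9.5. The plan's only design figure is for peak FEV1 and is used here just to fix n. It reproduces: SD = √ln(1 + 0.06²) = 0.0599; SE = 0.0599 × √(2/30) = 0.0155; ln(1.046) = 0.0450; power from the noncentral t with 29 df = 80.2%, against the stated 80%. The documents give no onset rates, so the true proportion p with onset by 120 minutes is an assumption, shown over a range.

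**One dose.** Take all patients as observed to 120 minutes, and let X be the number with onset, X ~ Bin(30, p). The results are withheld if more than 15 are censored, that is, if X ≤ 14.

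| Assumed p | P(X ≤ 14) = P(withheld) |
|---|---|
| 0.30 | 98.3% |
| 0.40 | 82.5% |
| 0.45 | 64.5% |
| 0.50 | 42.8% |
| 0.55 | 23.1% |
| 0.60 | 9.7% |
| 0.65 | 3.0% |

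With n = 36 the figures are similar: 85.4%, 43.4%, 22.0% and 8.3% at p = 0.40, 0.50, 0.55 and 0.60.

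**At the cut.** Fifteen onsets of 30 are shown (50.0%, exact 95% CI 31% to 69%); fourteen are withheld (46.7%, CI 28% to 66%). The data are almost the same. Among displayed results, the mean observed proportion is 0.53 when the true p is 0.40 and 0.55 when it is 0.45.

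**What stays estimable.** With more than half censored at 120 minutes, the median is generally not reached. The 25th percentile is reached once at least a quarter respond, which is 8 of 30. At p = 0.40, P(8 ≤ X ≤ 14) / P(X ≤ 14) = (0.8246 − 0.0435) / 0.8246 = 0.947. In about 95% of suppressed cases the 25th percentile, itself a planned output, could still be reported.

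**Per dose against pooled.** Assume onset rates of 30%, 45%, 55% and 65% for the four doses in ascending order.

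- Per dose, the chances of being withheld are 98.3%, 64.5%, 23.1% and 3.0%.
- Pooled, all four are withheld if fewer than 60 of 120 patient-doses show onset. The expected total is 30 × (0.30 + 0.45 + 0.55 + 0.65) = 58.5, and the exact sum of four independent binomials gives P(total ≤ 59) = 0.575. Within-patient correlation of 0.3 to 0.7 moves this only to 0.55–0.56.

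**Status coding.** SAP 15.2.3.2 explains STATUS(1) once as an onset event and once as a censored observation. Both cannot hold. If the wrong one is programmed, the curves are inverted, and so is the count that triggers the rule.

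**The case against.** The case for the rule has real substance. It is written in advance with a numeric cut, and the cut is not arbitrary: the protocol's Kaplan-Meier statistic is the median, which cannot generally be estimated beyond 50% censoring. Invoking the rule also tells the reader that more than half were censored, and protocol 9.1 requires deviations from the planned analysis to be detailed and justified in the study report. These points reduce the harm. They justify reporting the median as not reached; they do not justify removing the curve and the lower quartile.

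Several stronger readings are tempting, and the documents do not support them:

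- A reader might infer that the whole objective goes unreported. Only the Kaplan-Meier estimates and figure are withheld. The summary by treatment and the pairwise p-values against 3000 µg (15.2.3.2) are not expressly removed, although the SAP does not say what that summary contains without the estimates. The mean FEV1 change over time by treatment and day (15.1.3) is also still reported, so the early time course remains visible even if the timing of response does not.
- A reader might infer that fast doses are shown and slow ones hidden. The trigger is the fraction responding by 120 minutes. A dose with 45% onset, all at 5 minutes, would be withheld; one with 55% onset, all at 120 minutes, would be shown.
- A reader might infer that the count is pooled over doses. The SAP is silent, and the by-treatment summaries and the STRATA TREATMENT statement make a per-dose reading at least as natural.

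Onset is also a secondary Phase II endpoint with placebo excluded from its summaries, so no placebo-controlled claim rests on it.

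**Conclusion.** The point holds for the Kaplan-Meier results. Their display depends on the endpoint's own outcome, contrary to protocol 9.4.5 and SAP 15.2.3.2, and SAP 3.3 does not declare it. That conclusion rests on the text alone and needs no onset rate. The size does need one: for a dose with 30 patients and a true rate between 40% and 60%, suppression has a probability between about 82% and 10%. The 57.5% chance of losing all four curves requires both the pooled reading and the assumed 30/45/55/65% rates, so it illustrates the ambiguity and is not an expectation. Calling the rule selective reporting of the objective would go too far, because it is pre-specified and leaves other outputs in place. It is a reporting defect in a secondary endpoint that should be corrected.

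**What to change.** Delete the >50% censoring clause from SAP Part B 15.2.1.3. In 15.2.3.2, state that the Kaplan-Meier curve is always presented by dose, together with the number and percent of patients with onset by 120 minutes and the 25th, 50th and 75th percentiles. Report any percentile not reached as >120 min. Give STATUS(1) a single meaning that matches how PROC LIFETEST uses it.

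The cost is a short SAP edit and minor additions to one table. The LIFETEST code is already specified, and no new data or method is needed.

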15.2.2. MISSING DATA METHODS FOR SECONDARY EFFICACY VARIABLE(S)

No imputation will be applied.

15.2.3. ANALYSIS OF SECONDARY EFFICACY VARIABLES

15.2.3.1. Analysis of Secondary Variables 1, 2, 3, 4, 5 and 6

The secondary variables listed above will be analyzed by comparing the RPL554 treatment groups to each other and placebo by rejecting the null hypothesis described below at significance level $\alpha=0.05$ level (2-sided):

$$H_0: \mu_j = \mu_0 \text{ versus } H_1: \mu_j \neq \mu_0$$

Document: Z:\RPL554\AZA40375\Biostatistics\Documentation\SAP\Verona RPL554-DP-201 SAP v2.0 – Part B

Author: [name] / [name]

Version Number: 2.0

Version Date: [08JUL2019]

Template No.: CS_TP_BS016 Revision 5

Reference: CS_WI_BS005

Effective Date: 01Apr2018

Copyright © 2009, 2010, 2012, 2016, 2018 IQVIA. All rights reserved. The contents of this document are confidential and proprietary to IQVIA Holdings Inc. and its subsidiaries. Unauthorized use, disclosure or reproduction is strictly prohibited.

where μ_j and μ_0 are the mean change from Baseline for each parameter for each respective dose of RPL554 and placebo.

ANCOVA analyses will be implemented using the SAS® procedure MIXED as follows:

```
PROC MIXED DATA = ...;
  CLASS USUBJID PERIOD TREATMENT;
  MODEL CHG = TREATMENT PERIOD BASELINE;
  LSMEANS TREATMENT / CL DIFF;
  RANDOM USUBJID;
RUN;
```

where CHG = difference in log (parameter – baseline parameter)

TREATMENT = treatment group (Respective dose of RPL554, 150 μ g, 500 μ g, 1500 μ g and 3000 μ g and placebo)

PERIOD = treatment period (treatment period 1, 2, 3, 4 and 5)

BASELINE = log (baseline parameter)

USUBJID = subject ID

The primary comparison will be the contrast (difference in least squares mean [LSMEAN]) between 3000 μ g RPL554 and placebo. The parameter value and its baseline covariate will be log-transformed prior to analysis using natural logarithm. The difference between the two log (parameter) – log (baseline parameter). Therefore, the LSMEAN statement between treatments in the above PROC MIXED will provide the log of the contrasts. Prior to presentations, the antilog of these point estimates and associated 95% confidence intervals will be performed, giving ratios of geometric means on the linear scale. The 2-sided p-value for the exponential (exp)least squares mean, exp(LSM), ratio between each of the 2 treatment groups and placebo will be reported.

Summary statistics for each parameter will be presented for baseline, at point of interest (if applicable) and change from baseline by treatment group on patients with both assessments, on the original scale.

Document: Z:\RPL554\AZA40375\Biostatistics\Documentation\SAP\Verona RPL554-DP-201 SAP v2.0 – Part B

Author: [name] / [name]

Version Number: 2.0

Version Date: [08JUL2019]

Template No.: CS_TP_BS016 Revision 5

Reference: CS_WI_BS005

Effective Date: 01Apr2018

Copyright © 2009, 2010, 2012, 2016, 2018 IQVIA. All rights reserved. The contents of this document are confidential and proprietary to IQVIA Holdings Inc. and its subsidiaries. Unauthorized use, disclosure or reproduction is strictly prohibited.

15.2.3.2. Analysis of Secondary Variable 7

Onset of action will be summarized by treatment and a Kaplan-Meier plot illustrating time to onset constructed. The SAS® procedure LIFETEST, will be used as follows to calculate the median, 25th and 75th percentile:

```
PROC LIFETEST DATA=... OUTSURV =... CONFTYPE = LINEAR METHOD =  
KM ALPHA = 0.05 ALPHAQT = 0.05 PLOTS = (SURVIVAL (FAILURE NOCENSOR));  
    TIME ONSET*STATUS (1);  
    STRATA TREATMENT;  
RUN;
```

where ONSET = time to onset of action

TREATMENT = treatment group (Respective dose of RPL554, 150 μ g, 500 μ g, 1500 μ g and 3000 μ g)

STATUS (1) = indicates an event of onset of action

To calculate the mean difference to RPL554 3000 μ g, the SAS procedure LIFETEST will be carried for each treatment comparison pair individually.

If a patient does not have onset of action from pre-dose on Day 1 over the next 120 minutes (2 hours) the data will be censored at 120 minutes or if a patient prematurely discontinued before 120 minutes, the last available assessment time post-dose (1 indicates censored variables). Median differences to the highest dose (RPL554 3000 μ g) will be estimated and the p-value based on the PROC LIFETEST above (Wilcoxon signed rank sum test) between each treatment groups and the highest dose will also be presented.

15.2.3.3. Analysis of Secondary Variable 8

As described in [section 4.3](#), this SAP will not summarise the analyses related to the PK concentrations and parameters and this will be handled by a third-party vendor.

15.2.3.4. Analysis of Secondary Variable 9

Summary statistics of change from baseline will be presented at Days 1 to 7 of each treatment period by treatment group. In addition, all rescue medication used during the serial spirometry assessments(Days 1 and 7) will be listed to assess the accuracy of the FEV₁ recordings.

Document: Z:\RPL554\AZA40375\Biostatistics\Documentation\SAP\Verona RPL554-DP-201 SAP v2.0 – Part B

Author: [name] / [name]

Version Number: 2.0

Version Date: [08JUL2019]

Template No.: CS TP BS016 Revision 5

Reference: CS WI BS005

Effective Date: 01Apr2018

Copyright © 2009, 2010, 2012, 2016, 2018 IQVIA. All rights reserved. The contents of this document are confidential and proprietary to IQVIA Holdings Inc. and its subsidiaries. Unauthorized use, disclosure or reproduction is strictly prohibited.

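### The onset-of-action legend in SAP Part B 15.2.3.2 gives STATUS = 1 the opposite meaning to the printed code and the later text; if STATUS is built from the legend, the Kaplan-Meier result is inverted

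*SAP*

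**What the plan says.** Time to onset is secondary variable 7 in Part B. SAP Part B 15.2.1.3 defines the event: "Onset of action is defined as a >10% increase in FEV₁ from pre-dose on Day 1 over the next 120 minutes". It also gives the censoring rule: "Patients not experiencing an onset of action will be censored at 120 minutes (2 hours) or at time of premature discontinuation". The same section withholds the Kaplan-Meier estimates and figure when censoring is judged too heavy, with the threshold given as "number of patients with onset of action censored >50" percent. Protocol 9.4.5 names the summary wanted: "from the survival curves the median time to onset will be estimated".

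SAP Part B 15.2.3.2 then prints the PROC LIFETEST code, containing "TIME ONSET*STATUS (1"). The legend directly below it says "STATUS (1) = indicates an event of onset of action". The second paragraph after the legend, on patients who do not reach onset, says "1 indicates censored variables".

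**The concern.** One value of one variable cannot mark both an onset and a censored time. The clash is visible without any knowledge of SAS. The syntax only shows which line is out of step.

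What is at stake is a stated Part B secondary objective. The median, the quartiles, the plot and the p-values against 3000 µg all come from this one procedure. If STATUS were derived from the legend and passed to the printed code, the program would still run, because every time value is valid. It would estimate time to being recorded without onset instead of time to onset.

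**Working it through.** The documents give no figure on this point, so there is none to reproduce. The check is a comparison of the statements, followed by an illustration on assumed data.

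**1. The four statements side by side**

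| Place in SAP Part B | What it implies |
|---|---|
| 15.2.1.3, derivation | Patients without onset are censored (no numeric code given) |
| 15.2.3.2, TIME statement | 1 is censored: PROC LIFETEST treats the value in parentheses as the censored value |
| 15.2.3.2, legend | 1 is an onset |
| 15.2.3.2, second paragraph after the legend | 1 is censored |

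Three agree and the legend contradicts them.

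**2. Inputs to the illustration**

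- 30 patients on one dose. This is the number used in Protocol 9.5 and serves only to size the example.
- Assumed: 20 onsets, at 5, 15, 30 and 60 minutes in counts 5, 6, 5 and 4; 10 patients without onset, all followed to 120 minutes.
- Product-limit estimate: S(t) = product over event times of (1 − events / number at risk).

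**3. Intended coding (1 = censored)**

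- S(5) = 25/30 = 0.833
- S(15) = 19/30 = 0.633
- S(30) = 14/30 = 0.467, the first value at or below 0.5, so the median is 30 minutes
- S(60) = 10/30 = 0.333
- Censored: 10/30 = 33%

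**4. Legend coding (1 = onset) with the printed TIME statement**

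- The 20 onsets are censored at 5 to 60 minutes, so S stays at 1.00 up to 120 minutes.
- At 120 minutes 10 patients are at risk and all 10 count as events: S(120) = 1 − 10/10 = 0, and the median is 120 minutes.
- Censored: 20/30 = 67%

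**5. Range over assumed onset proportions** (30 patients, no early discontinuation)

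| Onsets | Counts at 5/15/30/60/90/120 min | Intended: censored; median | Legend: censored; median |
|---|---|---|---|
| 30 (100%) | 10/8/6/3/2/1 | 0%; 15 min | 100%; no events, no median |
| 24 (80%) | 8/6/4/3/2/1 | 20%; 30 min | 80%; 120 min |
| 20 (67%) | 5/6/5/4/0/0 | 33%; 30 min | 67%; 120 min |
| 12 (40%) | 3/3/2/2/1/1 | 60%; not reached | 40%; 120 min |

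**6. Effect on the 50% rule**

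If a proportion p has onset, intended censoring is 1 − p and legend censoring is p. If the rule is applied per dose to the derived STATUS variable, it reverses. It would withhold output when p exceeds 0.5 (first three rows) and allow it when p is below 0.5 (last row).

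**7. When the inverted median is not 120 minutes**

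Let m patients have no onset and let a patients have onset first seen at 120 minutes. Under legend coding those a patients are censored at 120 but are still at risk there, so S(120) = 1 − m/(a + m) = a/(a + m). With m = 1 and a = 2, S(120) = 2/3 = 0.67 and the median is not reached. This happens whenever a exceeds m. A patient without onset who discontinued early would become an event before 120 minutes.

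**The case against.** The best reply is that the intended analysis can be recovered from the SAP itself. The derivation section, the TIME statement and the later paragraph all point the same way, and the legend can be read as a loose label for the status token rather than a rival coding rule. This stands, and it makes the harm conditional on someone coding from the legend.

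A reader might infer that the legend is what a programmer will use, so that the analysis will be wrong. Nothing in the documents says which line governs the derivation.

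A reader might also infer that the inverted median is 120 minutes for any dose with at least one patient without onset. Step 7 shows that this is false: the SAP counts 2 hours as an onset timepoint, and it censors early discontinuers at their last available assessment.

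Two further points limit the risk. Under the 50% rule, the false 120-minute median in the 20-onset example might be withheld rather than reported, although wrongly losing the output is also a harm. And an onset curve that stays flat at zero until 120 minutes would look odd for a bronchodilator measured from 5 minutes, so the error might be noticed.

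Finally, the endpoint is secondary, placebo is left out of it, and SAP Part B 7.4 treats secondary tests as nominal. None of this removes the contradiction.

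**Conclusion.** The contradiction is real and the legend is the wrong line. It is an internal inconsistency in the specification of a secondary endpoint. The choice of method is not in dispute and the primary endpoint is unaffected.

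If STATUS is built from the legend, the result is inverted. In the 20-onset example the median goes from 30 to 120 minutes and apparent censoring from 33% to 67%, enough to trip the 50% rule wrongly. At 40% onset the rule fails in the other direction and lets through a median of 120 minutes where the true one is not reached.

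These sizes rest on assumed onset times, 30 patients per dose, no early discontinuation, and the rule being applied per dose to the derived variable. The SAP does not say how that count is made. The direction of the error does not depend on these assumptions. The point is worth correcting because the error is avoidable and would not stop the program.

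**What to change.** Replace the legend line in SAP Part B 15.2.3.2 with: `STATUS = 0 if onset (>10% increase) observed by 120 minutes, 1 if censored`. Keep `TIME ONSET*STATUS(1)` and the later paragraph as they are. Before output is released, check the derived STATUS variable, and the count used for the 50% censoring rule, against the listed onset times.

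The cost is one line of text and one programming check. The intended analysis does not change.
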